#### 4.1.2 *Treatment Period*

At the randomization visit, 75 patients in each group will receive either placebo or lanifibranor 800 mg/day or lanifibranor 1200 mg/day for 24 weeks.

#### 4.1.3 *Follow-up Period*

Safety of withdrawal from treatment groups is assessed during a 30-day assessment phase.

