**Figure 2: Lanifibranor Reduces Inflammation and Steatosis in a 3 Weeks MCD Model**

### IVA337 effect on inflammation

### IVA337 effect on steatosis

#### 1.4.2 Pharmacokinetics

Lanifibranor is considered as a class II compound as regard to the Biopharmaceutics Classification System (BCS) Guidance: high permeability and low solubility. It was evidenced in all tested species that lanifibranor absorption is dependent on the drug substance form and formulation, leading to a bioavailability in animals from 15% up to >80%. An enterohepatic recycling was evidenced, and a food effect was observed in human in the presence of high fat breakfast.

After oral administration in human, maximum plasma levels ( $C_{max}$ ) of lanifibranor were reached at about 1.0-3.5 h, and terminal plasma elimination half-life was around 10-15 h. Both Area Under the Curve (AUC) and  $C_{max}$  increased in a linear but slightly less than dose-proportional manner. Steady-state lanifibranor concentrations were generally achieved by Day 3 after daily dose administration, with no significant accumulation.

The mean apparent volume of distribution  $V_z/F$  ranged from 318 to 607 L in healthy subjects. Lanifibranor was extensively distributed in monkeys (~10 L/kg). IVA337 binds very highly to plasma proteins in all tested species (~99.9%) and no affinity to blood cells was observed. By autoradiography in rat, lanifibranor was shown to be mainly distributed in the excretory organs (liver, kidneys, lungs, gastrointestinal tract) and in placenta in pregnant rats with no affinity for the melanin tissues and with very limited central nervous system penetration.

Lanifibranor-related radioactivity elimination was mainly faecal (>85%) and the urinary excretion was minor (<7%) with a very low renal clearance. The excretion was essentially complete after 3 days.

AUC indicated approximately 23% of the radioactivity in plasma were related to lanifibranor, while 77% were related to its metabolites. Lanifibranor was observed *in vitro* to be metabolized either by enzymes of phase I (mainly via CYP isoforms CYP2C8, 2C19 and 3A4) and phase II (mainly via UGT 2B7, 1A1 and 1A3). No affinity of lanifibranor to uptake or efflux transporters as substrate was evidenced *in vitro*.

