#### 5.3.6 Follow-up Post-Treatment Visit, End of Study Visit (V4, Week 28)

A follow-up visit takes place 4 weeks after the end of treatment. The assessments to be performed are listed in the Schedule of Study Procedures (Table 1).

Blood sampling: Kits with supplies and instructions are provided for the safety and efficacy blood sampling.

Please observe the reporting requirements for AEs (see Section 6).

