## - Definitions:

Adverse events will be coded according to Medical Dictionary for Regulatory Affairs (MedDRA) and coded as treatment emergent (TEAE) / non-treatment emergent (non-TEAE) according to the following definitions. TEAEs are defined as events occurring on or after the day of first dose intake of study product and up to follow up visit. Additionally, events present before the first dose of study product, but worsening under treatment are considered as TEAEs. Although every effort will be made to establish the onset date and time, events with missing onset date will be considered as TEAEs. An AE that will not qualify as a TEAE will be considered as a Non-TEAE. Non-TEAES will be summarized separately from TEAES, and will be presented in the same manner as TEAES.

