**Lanifibranor tablets to be received up to the time of biopsy at week 24:**

The total number of lanifibranor tablets to be received is equal to:

- $((\text{Date of biopsy at week 24} - \text{Study first treatment intake date} + 1) \times 3)$  for patients receiving lanifibranor at the dose of 1200 mg
- $((\text{Date of biopsy at week 24} - \text{Study first treatment intake date} + 1) \times 2)$  for patients receiving lanifibranor at the dose of 800 mg

4.5.6.2 *Adverse Event data*

- **Treatment Emergent Adverse Event**

A Treatment Emergent Adverse Event (TEAE) corresponds to an Adverse Event (AE) that occurred on or after first dose of treatment up to 28 days post-last dose.

- **Treatment Emergent Adverse Events related to study treatment**

TEAE related to treatment is defined as a TEAE having a relationship to treatment equals to “Possibly related”, “Probably related” or with a missing relationship to study treatment.

Relationship equals to “Unlikely Related” will be considered as not related.

- **Non-Treatment Emergent Adverse Events (non-TEAEs)**

Non-TEAEs are AEs that occurred prior to treatment start.

- **Post-Treatment Adverse Events (PTAEs)**

PTAEs are AEs that occurred more than 28 days after end of treatment.

- **Serious Adverse Events**

By definition, a serious AE (SAE) is an AE that, at any time, fulfils one or more of the following criteria:

- results in death,
- is life threatening (the subject was at immediate risk of death at the time of the event; it does NOT refer to an event which hypothetically might have caused death if it were more severe),
- requires in-subject hospitalisation or prolongation of existing hospitalisation,
- results in persistent or significant disability/incapacity (substantial disruption of a person's ability to carry out normal life functions),
- is a congenital anomaly/birth defect,
- is any important medical event that may not be immediately life threatening or result in death or hospitalisation but, based upon appropriate medical judgment, may endanger the subject or may require intervention.

The seriousness of the event will be directly assessed by the investigator (specific variable within the AE database); therefore no derivation is needed.

- **Onset day**

Onset day is defined as the time between the first treatment intake date and AE onset date: (AE onset date – date of first intake + 1).

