#### 5.3.2 *Display of adverse events*

##### 5.3.2.1 *Overall summary of Treatment Emergent Adverse Events (TEAEs)*

The following summary statistics will be given in the safety set of patients by treatment group (Lanifibranor 800mg, lanifibranor 1200mg, lanifibranor all, placebo):

- Number (%) of patients with at least one **TEAE**
- Number (%) of patients with at least one **TEAE related to treatment**
- Number (%) of patients with at least one **TESAE**
- Number (%) of patients with at least one **TESAE related to treatment**
  
- Number (%) of patients with a **fatal TESAE**
- Number (%) of patients with a **fatal TESAE related to treatment**
  
- Number (%) of patients with at least one **mild TEAE**
- Number (%) of patients with at least one **moderate TEAE**
- Number (%) of patients with at least one **severe TEAE**
  
- Number (%) of patients with at least one **severe TEAE related to treatment**
- Number (%) of patients with at least one **severe TESAE**
- Number (%) of patients with at least one **severe TESAE related to treatment**
  
- Number (%) of patients with at least one **TEAE leading to treatment permanent discontinuation**
- Number (%) of patients with at least one **TEAE leading to treatment permanent discontinuation related to treatment**

Corresponding number of events will also be provided for each type of AEs.

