### 5.3.2.4 Analysis of Post-Treatment Adverse Events (PTAEs)

For PTEAEs, only a listing will be edited in the safety set of patients.

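### The follow-up phase is meant to assess safety of withdrawal, but no adverse-event table named in the SAP text is split at the last dose

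*Protocol*

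**What the plan says.** - **Purpose of follow-up.** Protocol 4.1.3: "Safety of withdrawal from treatment groups is assessed during a 30-day assessment phase". Protocol 5.3.6 times the visit that closes this phase: "A follow-up visit takes place 4 weeks after the end of treatment".
- **Protocol AE window.** Protocol 9.7.2 defines treatment-emergent AEs (TEAEs) as "events occurring on or after the day of first dose intake of study product and up to follow up visit". The same section plans a description of TEAEs by time to onset.
- **SAP AE window.** SAP 4.5.6.2 defines a TEAE as an event that "occurred on or after first dose of treatment up to 28 days post-last dose". Post-treatment AEs begin only after that: "PTAEs are AEs that occurred more than 28 days after end of treatment".
- **SAP outputs.** SAP 5.3.2.1 introduces the overall TEAE summary with "The following summary statistics will be given in the safety set of patients by treatment group", and SAP 5.3.2.2 gives system organ class and preferred term (SOC/PT) tables for the same class of events. Neither is divided at the last dose. For later events, SAP 5.3.2.4 says "For PTEAEs, only a listing will be edited in the safety set of patients".
- **Time to onset.** SAP 4.5.6.2 defines an onset day counted from first intake, but no table named in SAP 5.3.2 uses it. SAP 4.6, which lists changes from the protocol, does not report the omission.

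**The concern.** The protocol states a safety question for the period after stopping treatment, and AEs are collected at V4. A team that follows the SAP text would still produce no by-arm AE result for that period. Events in the first 28 days off drug are counted together with 24 weeks of on-drug events. Events on days 29 and 30, still inside the protocol's 30-day phase, go to a listing.

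An excess of events after stopping in one arm could then pass unnoticed in the any-TEAE row. Where it did show in a preferred term, the table would not reveal that the events began off drug. In the other direction, the tables read as on-treatment safety carry about four weeks of off-drug events.

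**Working it through.** **How much of the window is off drug.** A completer has 24 weeks on treatment and 4 weeks of follow-up, so follow-up is 4/28 = 14% of TEAE time. Protocol 1.4.2 gives a terminal half-life of about 10-15 h and says "The excretion was essentially complete after 3 days". Five half-lives at 15 h is 75 h, or about 3 days, which agrees. About 28 - 3 = 25 of the 28 days are therefore drug-free (25/28 = 89%).

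**Arm size.** The documents give no figure for off-drug AEs, so the only plan figure used is 75 per arm. Protocol 9.2 derives it from 10% v 30%, two-sided alpha 0.025 and 80% power. With unpooled variance, n = (2.241 + 0.842)² × (0.10×0.90 + 0.30×0.70) / 0.20² = 9.505 × 0.30 / 0.04 = 71.3, so 72. That is the stated figure before rounding to 75.

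**Dilution.** Let q be the on-drug risk, equal in both arms, and let r0 and r1 be the off-drug risks on placebo and drug, independent of on-drug events. Then:

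- pooled risk in an arm = 1 - (1 - q)(1 - r)
- pooled difference = (1 - q)(r1 - r0)

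The AE rates below are assumptions.

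| q | r0 v r1 | Off-drug difference | Pooled risks | Pooled difference |
|---|---|---|---|---|
| 2% | 2% v 10% | 8 points | 4.0% v 11.8% | 7.8 points |
| 50% | 2% v 10% | 8 points | 51.0% v 55.0% | 4.0 points |
| 65% | 2% v 10% | 8 points | 65.7% v 68.5% | 2.8 points |
| 75% | 2% v 10% | 8 points | 75.5% v 77.5% | 2.0 points |
| 2% | 5% v 15% | 10 points | 6.9% v 16.7% | 9.8 points |
| 30% | 5% v 15% | 10 points | 33.5% v 40.5% | 7.0 points |
| 70% | 5% v 15% | 10 points | 71.5% v 74.5% | 3.0 points |

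**Illustrative power** (75 per arm, nominal two-sided 5%, normal approximation; the SAP tests no AE counts):

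- 2% v 10%: about 54% in a separate table, about 6% in the pooled row at q = 65%.
- 5% v 15%: about 53% separately, about 6% pooled at q = 70%, and 46% pooled at q = 2%.

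**Check on the assumed 2%.** A 65% risk over 24 weeks at constant hazard implies 1 - 0.35^(1/6) = 16% over 4 weeks, so 2% off drug on placebo is optimistic. With 16% v 24%, the separate table has power of about 23%. The pooled difference at q = 65% is still 0.35 × 8 = 2.8 points. The shrinkage factor depends only on q; the power figures depend heavily on the assumed rates.

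**The case against.** A reader might infer that the SAP breaks a protocol promise. The documents do not support that. The protocol's own TEAE definition already runs to the follow-up visit, so the pooling is in both documents. Withdrawal safety is also not a separate objective in Protocol section 4 or SAP 3.1. The gap lies between the stated purpose of the phase and both AE definitions.

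A reader might also infer that off-drug safety is not analysed at all. That is wrong too:

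- Safety laboratory tests are described by arm at each visit (SAP 5.3.3.3), and weight and blood pressure through week 28 (SAP 5.3.3.4).
- ALT, AST, GGT, fasting glucose, HbA1c and the main lipids are collected at week 28. The repeated-measures model for them includes a within-arm contrast of week 24 with week 28 (SAP 4.1.5, 5.2.3.8-5.2.3.10).

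A transaminase or glucose rebound in completers would be visible there. These outputs contain no AEs, however, and SAP 4.1.6.3 leaves early stoppers' V4 data out of the week-28 descriptions.

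Three further objections have force:

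- **Preferred terms and event counts.** Dilution is slight for rare terms, and the SAP tables also give total event numbers, which the once-per-patient rule does not limit. What stands is that off-drug timing is not visible in either count.
- **Time to onset.** For completers, V3 is at week 24 ± 3 days, so onset after about week 24 is essentially off drug, and the protocol's time-to-onset description would come close to the split. It would not isolate off-drug events in early stoppers, because its clock starts at first intake, and the SAP text names no such table.
- **Biopsy.** The end-of-treatment biopsy is done at V3, and SAP 4.3.5 accepts it up to 14 days after last intake. An off-drug table would include biopsy-related events unless they are marked.

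The appended mock-up tables file was not available, so the statement about missing tables is limited to the SAP text.

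**Conclusion.** The point holds for adverse events. Under the SAP text, the purpose stated in Protocol 4.1.3 has no by-arm AE result, and days 29-30 of the protocol's phase reach only a listing. The size depends on the on-drug risk. With q between 50% and 75%, an 8-point off-drug excess appears as 4.0 to 2.0 points in the pooled row. At q = 2% it appears as 7.8 points, and mainly its timing is lost. A claim that pooling would hide any withdrawal effect goes too far.

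These figures assume equal on-drug risk in the arms, independence between periods, and AE rates that the documents do not supply. The power values are illustrations only. No efficacy conclusion or type I error is affected. The change is worth making because the trial states this safety purpose and already collects the dates needed to address it.

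**What to change.** In SAP 5.3.2:

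1. Keep the pooled TEAE tables as they are.
2. Add a supplementary by-arm display with two parts: onset from first to last dose, and onset after the last dose up to V4. For each, give patients with at least one event, SOC/PT, severe events and serious events. Cite Protocol 4.1.3 as the question that the second part answers.
3. For the second part, use as denominator the patients followed after their last dose, early stoppers included.
4. Flag biopsy-related events or show them separately, so that they are not read as withdrawal effects.
5. Reconcile the SAP's 28-day cut-off with the protocol's 30-day phase and V4 wording, so that every event in the stated phase has a defined place.

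The cost is SAP wording and one extra set of descriptive tables. Onset and last-dose dates are already defined in SAP 4.5.6, and no new data collection is needed.

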#### 4.1.4 *Patient management at the end of treatment*

The trial treatment is stopped after V3.

After the follow-up period (V4, 4 weeks after V3) the Investigator/hepatologists/general practitioner will decide according to each patient, the need to use the lifestyle changes recommendations whenever appropriate and treatment of comorbidities which may play a role in NASH such as, for example, diabetes and hyperlipidaemia.

If the study is positive there will be further trials for which these patients may be eligible.

#### 4.1.5 *Total study duration*

The total duration of the study is up to 38 months, i.e. at least 30 months of enrollment period and up to 8 months of patient participation.

## 4.2 **Study Population**

### 4.2.1 *Inclusion Criteria*

1. Adult subjects, age ≥18 years.
2. NASH histological diagnosis according to the currently accepted definition of both EASL and AASLD (62,66,67), requiring the combined presence of steatosis (any degree ≥ 5%) + lobular inflammation of any degree + liver cell ballooning of any amount, on a liver biopsy performed ≤ 6 months before screening in the study and confirmed by centralized reading during the screening period *and*
  - a. SAF Activity score of 3 or 4 (>2)
  - b. SAF Steatosis score ≥ 1

- c. SAF Fibrosis score: < 4.
3. Subject agrees to have a liver biopsy performed after 24 weeks of treatment.
  4. Compensated liver disease with the following hematologic and biochemical criteria before randomization:
    - ALT < 10xULN
    - Hemoglobin  $\geq$  110 g/L (11 g/dL) for females and  $\geq$  120 g/L (12 g/dL) for males
    - White blood cell (WBC) >  $2.5 \times 10^9/L$  ( $2.5 \times 10^3/\mu L$ )
    - Neutrophil count >  $1.5 \times 10^9/L$  ( $1.5 \times 10^3/\mu L$ )
    - Platelets >  $100 \times 10^9/L$  ( $100 \times 10^3/\mu L$ )
    - Total bilirubin < 35  $\mu\text{mol/L}$  (2.06 mg/dL). Patients with bilirubin  $\geq$  35  $\mu\text{mol/L}$  can be included if non-conjugated bilirubin in the setting of a Gilbert's syndrome.
    - Albumin > 36 g/L (3.6 g/dL)
    - INR < 1.4
    - Serum creatinin < 115  $\mu\text{mol/L}$  (1.3 mg/dL) (men) or < 97  $\mu\text{mol/L}$  (1.1 mg/dL) (women) or estimated glomerular filtration rate  $\geq$  60 mL/min/1.73m^2
  5. No other causes of chronic liver disease (autoimmune, primary biliary cholangitis, HBV, HCV, Wilson's,  $\alpha$ -1-antitrypsin deficiency, hemochromatosis, etc...) considered to have an impact on the patient's safety or on the efficacy evaluation.
  6. If applicable, have a stable type 2 diabetes, defined as HbA1c  $\leq$  8.5% and fasting glycemia <10 mmol/L (180 mg/dL), no introduction of new medication in the previous 6 months, and no new symptoms associated with decompensated diabetes in the previous 3 months. Minor modifications of anti-diabetic treatments or dosages are allowed if done in a context of stable type 2 diabetes, i.e. HbA1c  $\leq$  8.5% in the previous 6 months.
  7. Have a stable weight since the liver biopsy was performed defined by no more than a 5% loss of initial body weight.
  8. Negative pregnancy test or post-menopausal. Women with childbearing potential (i.e. fertile, following menarche and until becoming post-menopausal unless permanently sterile) must be using a highly effective method of contraception (i.e. combined (estrogen and progestogen containing) hormonal/ progestogen-only hormonal contraception associated with inhibition of ovulation, intrauterine device, intrauterine hormone-releasing system, bilateral tubal occlusion, vasectomised partner). The contraceptive method will have to be followed for at least one menstruation cycle after the end of the study
  9. Subjects having given her/his written informed consent.

#### 4.2.2 Exclusion Criteria

1. Evidence of another form of liver disease considered to have an impact on the patient's safety or on the efficacy evaluation.
2. History of sustained excess alcohol ingestion in the year before the pre-study treatment biopsy: daily alcohol consumption > 30 g/day (3 drinks per day) for males and > 20 g/day (2 drinks/day) for females.

3. Unstable metabolic condition: Weight change > 5% in the last three months, diabetes with poor glycemic control (HbA1c > 8.5%), introduction of an antidiabetic or of an anti-obesity drug or restrictive bariatric (weight loss) surgery in the past 6 months prior to screening.
4. History of gastrointestinal malabsorptive bariatric surgery within less than 5 years or ingestion of drugs known to produce hepatic steatosis including oral corticosteroids (at dose >5mg/day prednisone equivalent), estrogens (at doses greater than those used for hormone replacement or contraception), tamoxifen, methotrexate, tetracycline or amiodarone in the previous 6 months. Corticosteroids administered by routes other than oral are allowed. One short (<2 weeks) course of oral corticosteroids, more than 3 months before the pre-study treatment biopsy is also allowed.
5. Significant systemic or major illnesses other than liver disease, including congestive heart failure (class C and D of the AHA), unstable coronary artery disease, cerebrovascular disease, pulmonary disease, renal failure, organ transplantation, serious psychiatric disease, malignancy that, in the opinion of the Investigator, would preclude treatment with lanifibranor and/or adequate follow up.
6. HBs antigen >0, HCV PCR >0 (patients with a history of HCV infection can be included if HCV PCR is negative since more than 3 years), HIV infection.
7. Pregnancy or lactation or inability to adhere to adequate contraception in women of child-bearing potential.
8. Active malignancy except cutaneous basocellular carcinoma.
9. Any other condition which, in the opinion of the Investigator would impede competence or compliance or possibly hinder completion of the study.
10. Body mass index (BMI) >45 kg/m^2.
11. Type 1 diabetes and type 2 diabetic patient on insulin.
12. Diabetic ketoacidosis
13. Fasting Triglycerides > 300 mg/dL (3.39 mmol/L).
14. Hemostasis disorders or current treatment with anticoagulants.
15. Contra-indication to liver biopsy.
16. History of, or current cardiac dysrhythmias and/or a history of cardiovascular disease event, including myocardial infarction, except patients with only well controlled hypertension. Any clinically significant ECG abnormality reported by central ECG reading confirmed by the Investigator to be Clinically Significant.
17. Participation in any other investigational drug study within the previous 3 months.
18. Have a known hypersensitivity to any of the ingredients or excipients of the IMP including: Lactose monohydrate, Hypromellose, Sodium laurilsulfate, Sodium starch glycolate (type A), Magnesium stearate, Opadry™ II 85F18422
19. Be possibly dependent on the Investigator or the Sponsor (e.g., including, but not limited to, affiliated employee).
20. Creatine phosphokinase (CPK) >5 x ULN

21. Patient with history of well documented osteopenia. Patient treated with vitamin D and/or Calcium based supplements for preventive reasons can be included.

*(The criteria below are applicable only for patients who will undergo a MRI/LMS in selected centers)*

22. Claustrophobia to a degree that prevents tolerance of MRI scanning procedure. Sedation is permitted at discretion of Investigator.
23. Metallic implant of any sort that prevents MRI examination including, but not limited to: aneurysm clips, metallic foreign body, vascular grafts or cardiac implants, neural stimulator, metallic contraceptive device, tattoo, body piercing that cannot be removed, cochlear implant; or any other contraindication to MRI examination.

#### 4.2.3 *Prohibited concomitant medications*

**If not specified, the following treatment must be stopped at the latest before randomization**

- PPAR Gamma agonists, PPAR Alpha agonists (fibrates), ezetimibe
- Bile salts chelators, phytosterols, fish oils,
- Glucagon like peptide-1 receptor agonists (incl. liaglutide, exenatide),
- Insulin,
- Vitamins E (alpha-tocopherol),
- Anticoagulants (incl. warfarin, dabigatran, rivaroxaban, apixaban),
- Oral corticosteroids.

